10.4 Interim Analysis

No interim analysis is proposed.

10.5 Analysis of Study Endpoints

10.5.1 Primary Endpoint

The primary endpoint is the proportion of subjects without a histopathologic upgrade over the 36-months following randomization and will be summarized by study arm. The primary endpoint for each subject is dichotomous with success defined as having been observed to be free of histopathologic upgrade at Biopsy 2 33 to 39 months after randomization. Histopathologic upgrading occurs when a subject with ISUP Grade Group 1 prostate cancer, at randomization, is upgraded to Grade Group 2 or higher, or a subject with ISUP Grade Group 2 prostate cancer, at randomization, is upgraded to Grade 3 or higher as determined by BICR, at any post-randomization biopsy. Histopathologic status is determined by biopsy and will be assessed at the scheduled biopsy or at any biopsy that is taken during radical-prostatectomy or

other time-point. Subjects upgrading before 36 months, or those found as upstaged at Biopsy 2, or those not observed at 36 months (i.e., do not complete Biopsy 2 prior to 39 months post randomization) will be regarded as failures in the primary analysis.

The primary analysis null hypothesis, $H_0: \Omega \leq 1$, versus the alternative hypothesis, $H_A: \Omega > 1$; where Ω is the odds of success in the sipuleucel-T arm over the odds of success in the control arm. The Cochran-Mantel-Haenszel (CMH) test, stratified by ISUP Grade Group 1 or 2 and the number of biopsies showing the presence of disease prior to registration will be used to estimate the odds ratio, and will be computed using exact methods based on Monte Carlo computations due to the potential for small frequencies.

10.5.2 Secondary Endpoints

The subsequent prostate cancer treatment, if any, for each subject will be determined. The category of subsequent prostate cancer treatment will be identified (e.g., surgery, radiation, androgen deprivation therapy). Subjects initiating alternative intervention will be regarded as sipuleucel-T treatment failures. These data will be summarized descriptively and compared between study arms using the Cochran-Mantel-Haenszel test.

Quality of life data will be summarized descriptively and compared between study treatment arms and in the aggregate within the efficacy population.

Safety data will be summarized descriptively by study treatment arms and in the aggregate within the safety population.

10.5.3 Exploratory Endpoints

Immune response will be assessed at each specified time-point. Immune response variables will be evaluated to determine if there is a correlation between the measures of immune response and upgrade or other changes to the ISUP group grade of the subject's prostate cancer.

Subjects undergoing a radical prostatectomy will have the biopsy sample evaluated for histological status of the prostate cancer. Histopathologic change will be defined as any change in ISUP grade at baseline to an upgrade, no change in, or down-grade to a their ISUP baseline grade group designation, or to a status indicating no prostate cancer disease identified. These data will be summarized descriptively and compared between study arms.

Biopsy results will be assessed to determine the rate of negative biopsy results. This data will be summarized descriptively and compared between study arms.

PSA velocity will be calculated as the slope of the simple linear regression of the natural log of PSA versus time.

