4.3 Exploratory Endpoints

- To calculate the correlation of prostate tissue and peripheral immune responses as well as product parameters to sipuleucel-T efficacy
- To determine in the cohort of subjects having a radical prostatectomy the number subjects with an ISUP Grade Group change (up- or down-grade) determined by BICR from radical prostatectomy tissue histology in each study arm
- To measure the percentage of subjects with a negative biopsy at any post- randomization biopsy assessment in each study arm
- To compare the proportion of subjects with clinical risk group progression (e.g., Cancer of the Prostate Risk Assessment (CAPRA) and National Comprehensive Cancer Network (NCCN) prostate cancer risk groups) between study arms
- To calculate Prostate-specific antigen (PSA) velocity from randomization through study completion in each study arm
- To determine the association of prostate cancer tissue genomic profile and sipuleucel-T treatment

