Biopsy 1 will be administered between 12 and 18 months, and Biopsy 2 will be administered between 33 and 39 months post randomization. All hematoxylin and eosin (H&E) and special stained slides will be assessed for histopathologic grading by BICR. Slides from each biopsy will be considered as a group to determine the ISUP Grade Group as opposed to any single slide. The BICR is blinded to a subject's study arm randomization. BICR will receive the local pathology staining methods and Gleason score. All subject information should be redacted from the local pathology reports and slides. Local pathology reports and slides will be identified only by study subject number. All slides will be returned to the clinical trial site.

Post randomization, central pathology requested formalin-fixed paraffin-embedded (FFPE) tissue blocks identified by study subject number will be sent to the central pathology lab for cutting and slide preparation for immunohistochemistry (IHC) and genomic analysis. All tissue blocks will be returned to the clinical trial site.

Follow-up Phase:

Once a subject from either the sipuleucel-T or control arms completes the end of Active Phase visit, they will enter into Follow-up Phase and will complete Follow-up Phase visits every 6 months starting from their last Active Phase visit. The Follow-up Phase end when the last subject enrolled completes Biopsy 2 and end of Active Phase visit or until the study is terminated by the sponsor. All subjects will be assessed for:

[figure not shown]
- Survival status
- PROs/Quality of life questionnaires
- PSA levels (as available by local laboratory)
- Prostate cancer disease progression
- All anti-prostate cancer therapies
- AEs and SAEs (per reporting requirements for each arm; [Section 9](#))

P17-1 (ProVent) Protocol

Upon completion of the study, if the primary endpoint is met, subjects on the control arm may be offered sipuleucel-T.

The figure below presents a schematic of the study design.

Figure 1: Study Schematic

^a Epstein JI, Am J Surg Pathol, 2017

^b Weeks from **first infusion**; Sipuleucel-T arm only; 26 wk. & 6-mo. visit may occur same day

^c Months from **randomization in both arms**

^d Active Phase ends when the last subject enrolled completes 36-mo. Biopsy and end of Active Phase visit

^e International Society Urological Pathology (ISUP); Grade Group 1 = Gleason 3+3; Grade Group 2 = Gleason 3+4

^f Immunohistochemistry (IHC)

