6.7 Restricted Therapies During Sipuleucel-T Treatment Period

Certain therapies and procedures could confound the results of this study. Therefore, subjects who are randomized to the sipuleucel-T arm and receive any of the following, 30 days prior to the first infusion until 30 days after the last infusion, will discontinue sipuleucel-T treatment (Section 6.3.1):

- Any immunosuppressive therapy, including systemic steroids. Use of inhaled, intra-nasal, intra-articular, and topical steroids is allowed. Oral or IV steroids to prevent or treat IV contrast reactions are allowed
- Blood products
- GM-CSF or G-CSF
- Any vaccinations

Subjects that discontinue sipuleucel-T treatment and have received > 0 mL of sipuleucel-T will remain in the Active Phase and follow the schedule of events (Table 1).

6.8 Restricted Therapies from Randomization to End of Active Phase (Sipuleucel-T and Control Arms)

Certain therapies and procedures could confound the results of this study. Therefore, subjects who receive any of the following will go from Active Phase of the study to the Follow-up Phase of the study:

- Any local or systemic therapy or procedures for prostate cancer (e.g., ADT, radical prostatectomy, external beam radiation or brachytherapy)
- Any local or systemic therapy or procedure targeting the prostate (e.g., transurethral resection of the prostate (TURP) or 5-alpha reductase inhibitor)
- Major surgery at the discretion of the sponsor's Medical Monitor
- Any investigational product for prostate cancer or other condition (per sponsor's Medical Monitor approval)
- Any other therapy at the discretion of the sponsor's Medical Monitor

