7.3 Exploratory Endpoints

Per the protocol, the exploratory endpoints are:

- To calculate the correlation of prostate tissue and peripheral immune responses, as well as product parameters, to sipuleucel-T efficacy
- To determine in the cohort of subjects having a radical prostatectomy the number of subjects with an ISUP Grade Group change (up- or down-grade) determined by BICR from radical prostatectomy tissue histology in each study arm
- To measure the percentage of subjects with a negative biopsy at any post-randomization biopsy assessment in each study arm
- To compare the proportion of subjects with clinical risk group progression (e.g., Cancer of the Prostate Risk Assessment (CAPRA) and National Comprehensive Cancer Network (NCCN) prostate cancer risk groups) between study arms
- To calculate Prostate-specific antigen (PSA) velocity from randomization through study completion in each study arm
- To determine the association of prostate cancer tissue genomic profile and sipuleucel-T treatment

The interpretations of these exploratory endpoints are:

- Prostate tissue biomarkers, peripheral immune biomarkers, and sipuleucel-T product parameters by histological reclassification.
- Proportion of subjects with an ISUP Grade Group change (up- or down-grade) as determined by BICR from radical prostatectomy tissue histology in the cohort of subjects having a radical prostatectomy
- Proportion of subjects with a negative biopsy at any post-randomization biopsy assessment
- Proportion of subjects with clinical risk group progression (e.g., Cancer of the Prostate Risk Assessment (CAPRA) and National Comprehensive Cancer Network (NCCN) prostate cancer risk groups)
- Prostate-specific antigen (PSA) velocity from randomization through study completion
- Change in prostate cancer tissue genomic profile from baseline by treatment arm

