8.4.3 Clinical Laboratory Parameters

Table 1 shows the laboratory parameters that will be tested in this study. Only parameters tested by the central laboratory will be analyzed. Clinical laboratory data will be transferred from the central laboratory

and converted to International System (SI) units for analysis. Baseline laboratory parameters are those lab parameters collected closest in time, but prior to, randomization.

Table 1: Laboratory Parameters

HEMATOLOGY	CLINICAL CHEMISTRY
Hemoglobin (Hgb)	Total bilirubin
Hematocrit	Alkaline phosphatase
Red blood cell count (RBC)	Lactate Dehydrogenase (LDH)
White blood cell count (WBC)	Alanine aminotransferase (ALT/SGPT)
Absolute neutrophil count (ANC)	Aspartate aminotransferase (AST/SGOT)
Lymphocyte count	Blood urea nitrogen (BUN)
Monocyte count	Serum creatinine
Eosinophil count	Calcium
Basophil count	Magnesium
Platelet count	Glucose
OTHER BLOOD TESTS	Albumin
Total testosterone	Total Protein
Prostate-specific antigen (PSA)	Sodium
VIRAL SEROLOGY	Potassium
Human Immunodeficiency Virus (HIV-1 and HIV-2)	Bicarbonate
Hepatitis panel (HBsAg, HBsAb, HBcAb, HCV antibody (Ab), if Ab+ then HCV RNA))	Chloride
Human T-Lymphotropic Virus (HTLV-1, HTLV-2)	Phosphorus

The following laboratory abnormalities will be considered AEs and recorded in the subject's medical record and on the eCRF:

- Any clinically significant result that is not part of another reported clinical diagnosis
- Any result that meets the definition of an SAE
- Any result leading to discontinuation or interruption of sipuleucel-T
- Any result that requires therapeutic intervention or a change in subject management

Laboratory abnormalities that do not meet the above conditions will not be recorded on the eCRF.

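### PSA velocity is fitted to the end of the study with no stop at prostate therapy, so PSA values after treatment pull down the slopes of treated men

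*Protocol*

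**What the plan says.** - **Window.** Protocol 4.3 lists the endpoint as "To calculate Prostate-specific antigen (PSA) velocity from randomization through study completion in each study arm". SAP 7.3 interprets it as "Prostate-specific antigen (PSA) velocity from randomization through study completion".
- **Method.** Protocol 10.5.3: "PSA velocity will be calculated as the slope of the simple linear regression of the natural log of PSA versus time". The SAP adds no derivation in section 8 and no analysis in section 12.
- **What happens at therapy.** Under Protocol 6.8, "subjects who receive any of the following will go from Active Phase of the study to the Follow-up Phase of the study". The list opens with "Any local or systemic therapy or procedures for prostate cancer (e.g., ADT, radical prostatectomy, external beam radiation or brachytherapy") and goes on to other prostate-targeting treatment. SAP 6.1 likewise ends the Active Phase at that moment. The man stays on study.
- **PSA after therapy.** Follow-up assessments in Protocol 5.1 include "PSA levels (as available by local laboratory"), and Tables 1 and 2 footnote this PSA as locally analyzed. The phase lasts until the "last subject enrolled completes Biopsy 2 and end of Active Phase visit", unless the sponsor stops the study earlier.
- **Laboratory source.** SAP 8.4.3, under safety endpoints and variables, says "Only parameters tested by the central laboratory will be analyzed"; its table lists PSA.

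**The concern.** Surgery, radiation and ADT lower PSA directly. If values from before and after such treatment go into one straight line, the slope mainly records that the man was treated and when. It no longer measures how fast PSA rises under surveillance.

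A by-arm summary of these slopes then mixes disease behaviour with treatment uptake. Where treatment rates or timing differ between arms, the more-treated arm shows the lower velocity even if untreated PSA growth is identical. The stake is the reading of one exploratory endpoint.

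**Working it through.** The plan gives no figure for PSA velocity. Its design figures belong to the primary endpoint and play no part here. They do reproduce: the odds ratio is (0.84/0.16)/(0.70/0.30) = 2.25, and the sample size with continuity correction is 447 against the stated 450.

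**1. Do post-therapy values fall inside the window?** Yes. Therapy moves a man to Follow-up (Protocol 6.8), PSA is collected there (Protocol 5.1, Tables 1 and 2), and Follow-up lies before the end of the study. The rule in Protocol 10.5.2 that counts alternative intervention as treatment failure sits under the subsequent-treatment endpoint and does not touch PSA velocity.

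**2. Effect on one treated man.** All inputs are assumptions: ln(PSA) grows 0.10/year; PSA is taken at t = 0, 0.5, ..., 3.0 years; therapy follows the t = 1.5 value; PSA then stays at a fraction f of that value.

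- Mean t = 1.5, and Sxx = 2 × (1.5² + 1² + 0.5²) = 7.
- Against the untreated line, the values at t = 2, 2.5 and 3 shift by ln f − 0.10(t − 1.5).
- Change in slope = [(0.5 + 1 + 1.5) ln f − 0.10 × (0.25 + 1 + 2.25)]/7 = 0.4286 ln f − 0.05.
- Fitted slope b = 0.10 − 0.05 + 0.4286 ln f = 0.05 + 0.4286 ln f.

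If growth resumes at 0.10/year after the fall, b = 0.10 + 0.4286 ln f. If the window stops at therapy, the four values lie on the line and the slope is +0.10.

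| PSA falls to | b, flat after therapy | b, growth resumes | Stopped at therapy |
|---|---|---|---|
| 50% | −0.247 | −0.197 | +0.10 |
| 10% | −0.937 | −0.887 | +0.10 |
| 1% | −1.924 | −1.874 | +0.10 |

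For the flat case, varying growth over 0.05 to 0.20/year, therapy over months 15 to 30 and the last PSA at month 36 or 48 gives slopes from +0.03 to −1.95/year. Every one is below the true value.

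**3. Effect on the arm means.** With the same true slope in both arms and the same timing and fall among treated men, sipuleucel-T minus control = (share treated in control − share treated in sipuleucel-T) × (0.10 − b). Flat case:

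| Treated, sipuleucel-T vs control | Fall to 50% | Fall to 10% | Fall to 1% |
|---|---|---|---|
| 20% vs 20% | 0 | 0 | 0 |
| 15% vs 25% | 0.035 | 0.104 | 0.202 |
| 10% vs 30% | 0.069 | 0.207 | 0.405 |
| 25% vs 15% | −0.035 | −0.104 | −0.202 |

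If growth resumes, the 15% vs 25% row becomes 0.030, 0.099 and 0.197.

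**4. Does the laboratory rule settle it?** If SAP 8.4.3 governs this endpoint, locally analyzed Follow-up PSA drops out, and with it most post-therapy values. PSA at an Early Withdrawal visit carries no local-laboratory footnote and could remain. The same rule would also drop Follow-up PSA from untreated men, which contradicts a window running to the end of the study. The two texts give different data sets.

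**The case against.** The best counter-argument is SAP 8.4.3. Protocol 8.10 also assigns clinical laboratory tests, PSA among them, to a central laboratory. Collecting local PSA is not the same as analyzing it, so a programmer could fairly exclude it. That limits the problem but does not close it: the rule sits with safety laboratory parameters, is not linked to PSA velocity, and conflicts with the stated window.

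Second, no between-arm test is specified. Protocol 10.5.3 says that the prostatectomy and negative-biopsy results will be compared between arms, but not PSA velocity. This stands. A by-arm summary would still be read side by side.

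Third, a reader might infer that the endpoint is bound to point the wrong way when sipuleucel-T works, because control men would be treated more often. The documents do not support that. The hypothesis concerns upgrading, not treatment. Protocol 8.11 keeps upgraded men who stay on surveillance in the Active Phase. The cohort cited in Protocol 2.1.1 left surveillance more often for PSA doubling time (43.5%) than for grade progression (35%). Using the design upgrade rates of 16% and 30% as treated shares would replace one outcome with another.

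**Conclusion.** The point holds in a limited form. Followed as written, the endpoint definition takes in post-therapy PSA, and nothing in either document excludes it for this endpoint. Under the stated assumptions a treated man's slope moves from +0.10 to about −0.2 to −1.9/year. At 15% versus 25% treated, the spurious gap between arms is about 0.03 to 0.20/year. It vanishes when treatment is equal in rate and timing, and reverses if sipuleucel-T is the more-treated arm.

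The documents give no treatment rates by arm and no expected PSA falls, so neither size nor direction can be derived from them. PSA in Follow-up is taken only as available, so fewer post-therapy values may exist than the illustration assumes. This is a minor point about an exploratory endpoint.

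**What to change.** In the SAP:

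1. Compute PSA velocity from values up to the first prostate-directed therapy listed in Protocol 6.8.
2. Keep an all-values analysis as a sensitivity analysis, with a rule for PSA reported as zero or below quantification, since the logarithm of zero is undefined.
3. Reconcile SAP 8.4.3 with the endpoint window by stating which laboratory's values enter.

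A random-slope mixed model would suit unequal numbers of values per man, but it is optional; the window is what needs correcting.

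The cost is SAP wording, with no new visits or samples. Treated men contribute fewer values. If rising PSA prompts treatment, stopping at therapy truncates follow-up selectively, which is a reason to keep the all-values analysis beside it.

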10.5.4 Biomarker Analysis

The association of biomarkers with clinical response endpoints or survival may be assessed using appropriate statistical methods (e.g., analysis of variance [ANOVA], categorical or

survival models) depending on the endpoints. Other clinical covariates (such as baseline tumor characteristics and subject demographics) may also be included in the model. Association of biomarkers with clinical response or relevant time-to-event endpoints will also be explored in the overall population. Results of these exploratory analyses will be presented in separate technical reports.

10.5.5 Safety

The safety parameters to be analyzed are the incidence, intensity, and type of AEs, vital signs, clinical laboratory results, and limited physical examinations (abnormalities will be recorded as AEs ([Section 9.3](#))). Analysis of the safety parameters will be conducted on the safety population.

10.5.5.1 Adverse Events

AEs will be summarized and listed using the Medical Dictionary for Regulatory Activities (MedDRA version 18.0 or later) by preferred term within each body system. Tables to be produced will include the number and incidence of the following:

- Incidence within system organ class
- Incidence by decreasing frequency
- Incidence by NCI CTCAE (most current version) severity grade, by decreasing frequency
- Incidence within 1 day of infusion
- Incidence of SAEs
- Incidence of AEs that resulted in premature discontinuation of study

AEs that occur multiple times for a subject will be counted only once per subject in incidence summary tables. In tables that enumerate AEs by severity, only the greatest severity for an AE occurring multiple times for a subject will be counted.

10.5.5.2 Clinical Laboratory Data

Clinical laboratory test results will be summarized by type of laboratory test. For continuous measurements, descriptive statistics will be calculated at baseline and for observed values and changes from baseline at each scheduled time point. The number and percentage of subjects with abnormal values will be summarized. The number and percentage of subjects with parameters with NCI-CTCAE toxicity Grade of ≥ 3 will be summarized. Shift in toxicity grade from baseline to the worst grade experienced by the subject during the study will be provided.

10.5.5.3 Other Clinical Assessments

Descriptive statistics of blood pressure (systolic and diastolic) values and changes from baseline will be summarized at each scheduled time point. Descriptive statistics of other vital signs

(body temperature, heart rate, respiratory rate) at baseline will also be summarized. The number and percentage of subjects with values beyond clinically important limits will be summarized.

Abnormal findings in physical examination will be recorded and summarized as AEs. Weight will be summarized and DRE results will be provided in a listing.

10.5.6 Other

10.5.6.1 Demographics and Baseline Characteristics

Demographic information and baseline disease characteristics will be summarized descriptively for the primary analysis population and the treated and safety populations.

10.5.6.2 Subject Disposition

The following subject disposition information will be summarized:

- Number of subjects in the primary analysis population
- Number of subjects in the treated population
- Number of subjects in the safety population
- Number of subjects who prematurely discontinued the study and the associated reasons for early termination

10.5.6.3 Sipuleucel-T Administration

The following leukapheresis and infusion information will be summarized for all registered subjects:

- Number of subjects who received a total of 0, 1, 2, or 3 infusions
- Reason(s) for not completing 3 infusions
- Number of subjects who receive a total of 0, 1, 2, 3 4, or 5 or more leukapheresis
- Number of subjects who receive a total of 3 leukapheresis and 3 infusions

10.5.6.4 Sipuleucel-T Product Parameters

Sipuleucel-T product parameters (TNC count, APC count, and APC activation) will be summarized by Infusion 1, 2, 3, cumulative through Infusion 2, and cumulative through Infusion 3.

